7. DISCONTINUATION OF STUDY INTERVENTION AND PARTICIPANT DISCONTINUATION/WITHDRAWAL

7.1. Discontinuation of Study Intervention

A participant's investigational study intervention (JNJ-3989/placebo) **must** be discontinued if any of the criteria listed below apply. In those cases, NA treatment should be continued.

- The participant withdraws consent to receive study intervention.
- The investigator believes that for safety reasons or tolerability reasons (eg, AE) it is in the best interest of the participant to discontinue study intervention.
- The participant becomes pregnant.
- The participant has a \geq grade 3 rash (see Section 10.5, Appendix 5, Rash Management) or allergic reaction (see Section 8.3.6.3).
- The participant has signs of hepatic decompensation (ie, clinical evidence of ascites, bleeding varices, or hepatic encephalopathy) or an increase in direct bilirubin $>1.5x$ ULN in combination with INR $\geq 1.5x$ ULN or albumin <3.0 g/dL. In this case treatment with JNJ-3989 should be discontinued and alternative treatment options (outside the study) should be considered in discussion with the sponsor.

- The participant has a confirmed \geq grade 3 estimated glomerular filtration rate (eGFR) abnormality and a drop from baseline of >10 mL/min/1.73 m², considered at least possibly related to JNJ-3989 that persists despite change of tenofovir disoproxil to ETV or TAF (if the patient was receiving tenofovir disoproxil). Change of NA treatment should be considered anytime, according to the prescribing information. (see Section 8.3.6.4).
- The participant has a confirmed QTcF prolongation (defined as a QTcF value of >500 ms, or an increase from baseline of >60 ms) at any given time point.
- The participant requires treatment with any of the disallowed medications listed in Section 6.7 and does not intend to discontinue treatment with the disallowed medication.
- The participant has confirmed HBV virologic breakthrough (ie, confirmed on-treatment HBV DNA increase by >1 log₁₀ IU/mL from nadir or confirmed on-treatment HBV DNA level >200 IU/mL in participants who had HBV DNA level $<$ LLOQ of the HBV DNA assay). In case of virologic breakthrough, changing the NA should be considered in consultation with the sponsor. Injection with JNJ-3989 will be stopped if the NA change does not result in a decrease in HBV DNA levels.
- The participant has ALT/AST elevations, as described in Section 8.3.6.1, Intervention-emergent ALT/AST Elevations.
- Per IDMC recommendation, in Part 2, the participants with HBsAg values >10.000 IU/mL at screening or baseline, who were assigned to Arm 1 (placebo), will not roll-over to the open-label phase and will enter the follow-up phase.
- The participant of the placebo group should discontinue study intervention (cannot start JNJ-3989 in the open-label phase in Part 2, Arm 2) if he/she develops cirrhosis at the end of the double-blind phase (based on the Week 48 FibroScan assessment).

If a participant discontinues study intervention for any reason before the end of the double-blind phase, end-of-intervention assessments must be obtained. The participant will enter the follow-up phase and complete the follow-up schedule unless the participant withdraws consent. Participants who withdraw consent will be offered an optional safety follow-up visit (see Section 1.3). Study intervention assigned to the participant who discontinued study intervention may not be assigned to another participant.

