- Following local standard practice, the biopsy location will be identified with ultrasound (which will also be used to rule out contraindicating conditions for a biopsy). Prior to any on-treatment biopsy, a recent (≤ 1 week) coagulation and hematology panel are required (pre-biopsy visit) to ensure normal platelet count and normal coagulation parameters. Prior to the baseline or off-treatment biopsies, blood coagulation and platelet count will be assessed according to local practice. Site selection will be based on their experience in the performance of core liver biopsies and FNABs.

- Unblinding of the Part 2 double-blind phase laboratory data for HDV RNA and HBsAg data (Day 1 to Week 48 visit) per investigator's request at any time prior to Week 48 visit to the investigator, in case this is required for medical/clinical patient management.
- Unblinding of the double-blind phase in Part 2 for treatment allocation and all laboratory data including HDV RNA and HBsAg data (Day 1 to Week 48 visit) when a participant has completed the Week 48 visit or discontinued earlier, to the investigator, site personnel, sponsor, and participants.
- In Part 2, participants with HBsAg values >10,000 IU/mL at screening or baseline, who were assigned to Arm 1 (placebo), will not roll-over to the open-label phase and will enter the follow-up phase (see Section 7.1).

Any clinically significant abnormalities persisting at the end of the study/early discontinuation will be followed up by the investigator until resolution (return to baseline) or until stabilization (to be agreed upon with the sponsor).

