An IDMC will be established for continuous monitoring of SAEs, AEs leading to discontinuation, and ALT flares. In addition, the IDMC will support the Sponsor Committee in assessing whether there is early evidence supporting antiviral activity criteria of JNJ-3989 + NA in reducing HDV replication measured by HDV RNA reduction. Before Part 1 IA1, the Sponsor Committee, who is not directly involved in the study conduct, will be involved in the unblinded review of selected efficacy and safety parameters to decide when to trigger the start of Part 2. At the time of the Part 1 IA1 (when all participants of Part 1 have completed at least Week 16 or discontinued earlier), the sponsor, including the Sponsor Committee, will become unblinded to the Part 1 data. Once Part 2 has commenced, all sponsor personnel, including the Sponsor Committee, will remain blinded to subsequent IDMC data review during the double-blind phase. During the open-label phase, all data will be unblinded. When all participants are in the open-label phase or discontinued earlier, the IDMC responsibilities will be covered by the DRC (see Sections 9.5.4 and 10.3.6).

Before Protocol Amendment 5, Part 1 and Part 2 include 3 identical phases:

- a 4-week screening phase (may be extended up to a maximum of 8 weeks^a),
- a 144-week study intervention phase (Arm 1) and 148-week study intervention phase (Arm 2). The first 52 weeks of the intervention phase are double-blind followed by 92 and 96 weeks of open-label treatment for participants in Arms 1 and 2, respectively.
- a 48-week follow-up phase.

Per Protocol Amendment 5, Part 2 will include modified phases after screening:

- a 4-week screening phase (may be extended up to a maximum of 8 weeks^a),
- for both Arm 1 and Arm 2, the double-blind 52 weeks of intervention will be followed by an open-label phase of at least 48 weeks of JNJ-3989 for all participants, including for those participants who were randomized to placebo in the intervention phase. Arm 1 will have a total minimum of 96-week intervention and Arm 2 a total minimum of 100-week intervention.
- a reduced follow-up phase (at least 24 weeks):
 - for participants who have reached FU Week 24 or later when Protocol Amendment 5 is in effect, the EOS assessments will be scheduled at the next planned visit; *OR*
 - for participants who have not reached FU Week 24 (including participants in the open-label phase) when Protocol Amendment 5 is in effect, they will enter a 24-week follow-up phase.

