- Arm 2: placebo for JNJ-3989 (SC injection Q4W) + NA qd for 52 weeks, followed by 100 mg JNJ-3989 (SC injection Q4W) + NA qd for 96 weeks (n 4; deferred active treatment arm).

NA nucleos(t)ide analog ETV, tenofovir disoproxil, or TAF. NA treatment is continued or started from Day 1 in both arms.

Part 2

Part 2 of the study will be initiated since the antiviral activity criteria in Part 1 have been met, and the results of Part 1 IA1 (when all participants of Part 1 have completed at least Week 16 or discontinued earlier) support initiation of Part 2. Cirrhotic participants will be excluded from participation in Part 2 of the study.

Approximately 30 participants co-infected with HBV and HDV will be randomized in a 4:1 ratio to Arms 1 or 2.

- Arm 1: 100 mg JNJ-3989 (SC injection Q4W) + NA qd for at least 96 weeks (approximately, n 24; immediate active treatment arm);
- Arm 2: placebo for JNJ-3989 (SC injection Q4W) + NA qd for 52 weeks, followed by 100 mg JNJ-3989 (SC injection Q4W) + NA qd for at least 48 weeks (approximately, n 6; deferred active treatment arm).

NA ETV, tenofovir disoproxil, or TAF. NA treatment is continued or started from Day 1 in both arms.

Study Details

In total across both Part 1 and Part 2, a target of approximately 50 participants, aged ≥ 18 to 65 years, co-infected with HDV and HBV will be enrolled in this study. If Part 2 is not initiated, the number of participants will be approximately 20.

Patients with HBV/HDV co-infection will be eligible regardless of HBeAg status and treatment history. Patients with compensated cirrhosis are only allowed to be enrolled in Part 1 of this study. Cirrhotic patients will be excluded from participation in Part 2 of the study.

Randomization will be stratified by:

- presence of compensated cirrhosis at screening (yes or no) (Part 1 only),
- HDV RNA testing laboratory location (China versus outside of China) (Note: All sites in China will utilize the laboratory testing in China and all sites in other countries will utilize the laboratory outside of China), and
- HBeAg status at screening (positive versus negative).

In those countries/sites where HDV testing is not part of standard of care, possible study candidates can be prescreened for HDV testing (HDV RNA and/or anti-HDV antibody) after signing a prescreening informed consent form (ICF). Results will be reviewed by the investigator to confirm if they could qualify for study participation.

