9.4.2.1. Primary Estimand

The main analysis of the primary endpoint will be addressed by using the following estimand attributes:

1. Study Intervention:

- Arm 1: JNJ-3989 + NA
- Arm 2: Placebo + NA

2. Study population: Participants 18 to 65 years of age, inclusive, with HBV/HDV co-infection

3. Variable: Response status defined as having HDV RNA decline $\geq 2 \log_{10}$ IU/mL from baseline or HDV RNA TND in combination with normal ALT at Week 48

4. Intercurrent events (ICEs):

- a. Treatment discontinuation prior to Week 48: if the participant discontinued treatment prior to Week 48 then the participant will be considered as non-responder (composite strategy).
- b. Selected major protocol deviations (identified as ICEs): participants who experienced major protocol deviations considered ICE and who have missing ALT and/or HDV RNA data for the primary endpoint at Week 48 will be considered as non-responders (composite strategy).
- c. Deaths prior to Week 48 are handled in a composite strategy as participants who die prior to Week 48 will be considered as non-responders.

5. Population level summary: Difference in proportion of responders between the 2 intervention arms (Arm 1-Arm 2).

Note: The SAP will list the major protocol deviations used for the purpose of efficacy analyses and flag those that are to be considered ICEs.

Assumptions:

- Missing Data for HDV RNA and ALT are Missing At Random (MAR)
- The treatment effect is homogeneous across strata.

Data Included

All available data from randomized participants that have received at least one dose is included (ITT analysis set in Part 2), after taking into account all the ICEs and applying the ICE strategies.

Missing Data Handling Rules

Participants who withdraw from the study prior to Week 48 will be considered as non-responders.

If a participant remains in the study after early discontinuing treatment or after experiencing a major protocol deviation (defined for the purpose of efficacy analyses and is an intercurrent event) and has missing Week 48 value for HDV RNA and/or ALT, then the imputation to non-response will be applied. If the value for the primary endpoint at Week 48 is available, then such data will be used to determine their response status.

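### The Part 2 roll-over bar for high HBsAg pairs Arm 1 with placebo, although Arm 2 is the placebo arm, and Sections 1.1, 4.1 and 4.2 do not reflect the bar

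*Protocol*

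**What the plan says.** The roll-over bar stands twice in the current text. Section 7.1 places it in the list of reasons for which investigational treatment must be discontinued, attributes it to the IDMC, and words it as "in Part 2, the participants with HBsAg values >10.000 IU/mL at screening or baseline, who were assigned to Arm 1 (placebo), will not roll-over" (into open-label treatment). Section 2.3.3 lists it among the measures that reduce risk: "In Part 2, participants with HBsAg values >10,000 IU/mL at screening or baseline, who were assigned to Arm 1 (placebo), will not roll-over", with the participants concerned entering follow-up instead.

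The Part 2 arms are defined in Section 4.1, with the same assignment in the synopsis: "Arm 1: 100 mg JNJ-3989 (SC injection Q4W) + NA qd for at least 96 weeks" and "Arm 2: placebo for JNJ-3989 (SC injection Q4W) + NA qd for 52 weeks", the latter followed by deferred JNJ-3989. The primary estimand in Section 9.4.2.1 agrees: "Arm 2: Placebo + NA".

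On who receives open-label treatment, Sections 1.1 and 4.1 promise both arms the following: "open-label phase of at least 48 weeks of JNJ-3989 for all participants, including for those participants who were randomized to placebo in the intervention phase". Section 4.2 states that placebo participants switch to JNJ-3989 at Week 52 and that the deferred design lets every participant receive the regimen. Footnote z of the double-blind Schedule of Activities (Section 1.3.1) also has Arm 2 switching at Week 52. None of these places mentions the HBsAg exception.

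**The concern.** A rule that decides who may start or continue an investigational drug should identify its group without ambiguity. This one names the group twice, by number and by treatment, and the two do not match. Someone applying or programming it by arm number reaches the JNJ-3989 arm; someone applying it by treatment name reaches the deferred arm. The rule has a safety purpose: Section 2.3.1.2 reports a higher risk of confirmed ALT elevations above 10,000 IU/mL HBsAg in Part 2.

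The bar also affects the summaries. A deferred-arm participant who is held back goes into follow-up without ever having received JNJ-3989. Section 3 has endpoints for sustained response and for relapse after the end of JNJ-3989 treatment, and Sections 9.4.4 and 9.4.6 summarise by arm and phase. If the design sections are taken at face value, every Arm 2 participant who reached Week 52 would be counted as exposed.

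**Working it through.** No power or sample-size figure is involved. The check sets the sections side by side and adds short arithmetic.

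**1. Arm label**

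| Place in the protocol | Arm 1 | Arm 2 |
|---|---|---|
| Sections 1.1 and 4.1, arm definitions | JNJ-3989 + NA | placebo + NA, then JNJ-3989 |
| Section 9.4.2.1, estimand | JNJ-3989 + NA | placebo + NA |
| Section 7.1, bullet on cirrhosis at Week 48 | not mentioned | placebo group |
| Sections 2.3.3 and 7.1, HBsAg bar | placebo | not mentioned |

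The last row conflicts with all the others. The cirrhosis bullet directly follows the HBsAg bullet, so Section 7.1 disagrees with itself across two adjacent items.

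**2. Threshold notation**

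- Section 7.1 prints 10.000 IU/mL.
- Section 2.3.3 (same rule), Section 2.3.1.2 (ALT risk) and Section 5.1, criterion 5.1 (Part 2 entry) print 10,000 IU/mL.

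Three places against one, with commas used for thousands there, point to a notation slip in Section 7.1.

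**3. Can the bar apply to anyone?**

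Yes. Criterion 5.1 admits Part 2 participants above 10,000 IU/mL if screening HDV RNA is at most 100,000 IU/mL. The exception is therefore not empty by design, although the protocol does not say how many participants it touched.

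**4. Open-label duration**

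Open-label weeks = total intervention weeks - 52 double-blind weeks. The protocol's own figures before Amendment 5 confirm this counting:

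- Arm 1: 144 - 52 = 92, as stated.
- Arm 2: 148 - 52 = 96, as stated.

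Applied to the Amendment 5 minima in Sections 1.1 and 4.1:

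- Arm 1: 96 - 52 = 44, against at least 48 stated (4 weeks short).
- Arm 2: 100 - 52 = 48, as stated.

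The 48-week statement fits Arm 2 only. Arm 1's total JNJ-3989 period is still 52 + 44 = 96 weeks, so the mismatch lies in the description of the open-label phase and not in that total.

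**5. Timing and scale**

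The Amendment 5 rationale puts everyone beyond the double-blind phase. Part 2 stood at 11 completed, 17 in open-label treatment and 2 in follow-up: 11 + 17 + 2 = 30, the full Part 2 enrolment. The roll-over point had passed for all of them. Arm 2 of Part 2 was planned at about 6, so a single participant is 1/6, or about 17%, of that arm. This is a scale per participant; the number withheld is not given and could be zero.

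**The case against.** The strongest reply is that nothing can go wrong any more. Roll-over is decided at Week 52 and every participant is past it. Both statements of the bar contain the word placebo, the next bullet locates the placebo group in Arm 2, and allocation is unblinded once a participant completes Week 48 (Sections 4.1 and 6.3), so a site knew what each participant had received. This stands, and it removes any forward-looking risk. A reader might infer that the wrong participants were stopped or started; the protocol contains no evidence that the rule was misapplied.

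A reader might also take 10.000 as ten and see a thousandfold difference in the threshold. The context does not support that reading.

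It can be said that Sections 4.1 and 4.2 give the planned course, that Section 7.1 lists overriding exceptions, and that Section 4.1 itself provides for premature discontinuation. That is fair for individual stopping events. It is weaker for a bar fixed in advance by screening or baseline HBsAg, when the text expressly includes those randomised to placebo.

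Finally, denominators are commonly settled in the SAP, which was not available for this point, and endpoints worded as following the end of JNJ-3989 presuppose exposure. Their absence from the protocol is therefore not itself a fault. The separate summary is recommended because the design text describes exposure that some Arm 2 participants may not have had.

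**Conclusion.** The point holds as an internal inconsistency in current protocol text. The arm number and treatment name in the HBsAg bar disagree in both places where it appears. The design sections do not carry the exception, and the 48-week open-label minimum is 4 weeks too long for Arm 1. The threshold notation is minor.

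The consequence is limited. The value of a correction lies in an accurate record, in confirming that past roll-over decisions followed the intended rule, and in correct open-label and follow-up summaries. The primary and key secondary endpoints are measured at Week 48, before roll-over, and are not affected; a reader should not infer bias in them. All analyses are descriptive (Section 9.1).

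This rests on the participant status given in the Amendment 5 rationale and on counting open-label weeks from Week 52, as the protocol does. It takes no position on which clinical rule, group or threshold should apply; that is for the sponsor to confirm against the IDMC recommendation.

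**What to change.** Reconcile Sections 1.1, 2.3.3, 4.1, 4.2 and 7.1, together with footnote z of Section 1.3.1, so that the arm number, treatment name, threshold notation, the exception and the open-label durations by arm all agree. A clarification letter or the next amendment would do.

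Check the Part 2 roll-over decisions already taken against the confirmed rule and document the result, including how many participants were held back.

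In the analysis, flag Arm 2 participants who never received JNJ-3989. Summarise them separately from the denominators for open-label results and for endpoints defined after the end of JNJ-3989 treatment. If the SAP already does this, a cross-reference is enough.

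The cost is an editorial correction, a review of at most 30 participant records, and one analysis flag. No new data are needed.

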7.2. Participant Discontinuation/Withdrawal From the Study

A participant will NOT be automatically withdrawn from the study if he or she has to discontinue study intervention.

A participant will be withdrawn from the study for any of the following reasons:

- Lost to follow-up
- Withdrawal of consent
- Death

When a participant withdraws before study completion, the reason for withdrawal is to be documented in the CRF and in the source document. If the reason for withdrawal from the study is withdrawal of consent then no additional assessments are allowed.

Withdrawal of Consent

A participant declining to return for scheduled visits does not necessarily constitute withdrawal of consent. Alternate follow-up mechanisms that the participant agreed to when signing the consent form apply as local regulations permit.

7.2.1. Withdrawal From the Use of Research Samples

A participant who withdraws from the study will have the following options regarding the optional research samples (ie, host DNA samples):

- The collected samples will be retained and used in accordance with the participant's original separate informed consent for optional research samples.
- The participant may withdraw consent for optional research samples and may request destruction of the previously collected samples, in which case the samples will be destroyed and will not be used further. To initiate the sample destruction process, the investigator must notify the sponsor study site contact of withdrawal of consent for the optional research samples and to request sample destruction. The sponsor study site contact will, in turn, contact the biomarker representative to execute sample destruction. If requested, the investigator will receive written confirmation from the sponsor that the samples have been destroyed.

Withdrawal from the Optional Research Samples While Remaining in the Main Study

The participant may withdraw consent for optional research sample while remaining in the study. In such a case, the optional research samples will be destroyed. The sample destruction process will proceed as described above.

Withdrawal from the Use of Samples in Future Research

The participant may withdraw consent for use of samples for research (refer to Long-Term Retention of Samples for Additional Future Research in Section 10.3, Appendix 3: Regulatory, Ethical, and Study Oversight Considerations). In such a case, samples will be destroyed after they are no longer needed for the clinical study. Details of the sample retention for research are presented in the main ICF and in the separate ICF for optional research samples.

7.3. Lost to Follow-up

A participant will be considered lost to follow-up if he or she repeatedly fails to return for scheduled visits and is unable to be contacted by the study site. A participant cannot be deemed lost to follow-up until all reasonable efforts made by the study-site personnel to contact the participant are deemed futile. The following actions must be taken if a participant fails to return to the study site for a required study visit:

- The study-site personnel must attempt to contact the participant to reschedule the missed visit as soon as possible, to counsel the participant on the importance of maintaining the assigned visit schedule, to ascertain whether the participant wishes to or should continue in the study.
- Before a participant is deemed lost to follow-up, the investigator or designee must make every reasonable effort to regain contact with the participant (where possible, 3 telephone calls, e-mails, fax, and, if necessary, a certified letter to the participant's last known mailing address, or local equivalent methods). These contact attempts should be documented in the participant's medical records.
- Should the participant continue to be unreachable, they will be considered to have withdrawn from the study.

